**Protocol Approved By:**

PRINCIPAL INVESTIGATOR:

EXECUTIVE SPONSORS:

\_\_\_\_\_  
[name]

\_\_\_\_\_  
Print Name

\_\_\_\_\_  
Date

\_\_\_\_\_  
Signature

\_\_\_\_\_  
Print Name

\_\_\_\_\_  
Signature

PROTOCOL SUMMARY	
Study Title	HIIN – BH: An evaluation of Emergency Department to admission conversion among patients with a telepsychiatric consult who are followed by a behavioral health - virtual patient navigation team
Study Design	A randomized, quality improvement evaluation
Study Objectives	
The primary objective is to evaluate the effect of a behavioral health virtual navigation team compared to usual care among patients with a telepsychiatric consult, on Emergency Department to inpatient conversion.
 
Secondary objectives of the evaluation include: Compare the following between the intervention group and the usual care group:
 
 
○ 45-day post discharge utilization (ED, inpatient, and observation encounters)
 
○ 90-day post discharge utilization (ED, inpatient, and observation encounters)
 
○ CHS Quality, Comfort, and Care defined 30-day readmission rate. This is a readmission rate among patients with an inpatient readmission to the same CHS facility as the index encounter.
 
○ The patient-centric defined 30-day readmission rate. This is a readmission rate among patients with an inpatient or observation readmission to any CHS facility.
 
 
Additional analyses will be to explore:
 
 
a. As a sub-analysis, qualitative outcomes will be collected and measured with patients, providers, and leaders. These outcomes will be collected and evaluated, per a sub-study protocol addendum.
 
b. Historical health records may be pulled to explore baseline rates of risk factors among prior behavioral health patients at CHS.
 

Inclusion/ Exclusion Criteria	
Inclusion:
 
 
● 18 years of age or older
 
● ED visit
 
● Completed telepsychiatric consult at the ED visit
 
● Telepsychiatric consult occurs Monday through Friday during the Navigator’s potential hours of operation
 

Study Procedures	Patients who present to the ED at one of the two participating CHS EDs with a telepsychiatric consult performed will be treated and followed per the proposed CHS behavioral health patient navigation pathway (BH-VPN) or usual care. As part of the current care process, Patients are identified by the ED physician in the ED as needing psychiatric evaluation and a referral is made to the telepsychiatric consult, the care of these patients will follow the allocated BH-VPN pathway or

	
usual care. Regardless of participation in the BH-VPN pathway or usual care, the ED providers decide based on available information the ultimate disposition for patients --discharge from the ED or admit to the hospital.
 
Patients who complete a telepsychiatric consult in the ED Monday through Friday during the hours of operation can be enrolled to either the control or intervention arm based on a randomization scheme that randomly allocates days that navigators are available. On days where the navigator is available, all patients who meet eligibility criteria will be considered exposed to the interventions; whereas, on days the navigator is not available all patients will be considered exposed to Usual care. Patients who are in the intervention arm will be offered navigation services for 45 days following ED discharge.
 
The BH-VPN pathway is defined by several key components:
 
 
• Introduction of the navigation process to the patient, while in the ED
 
• Evaluation of the patient and their needs.
 
• Follow-up evaluation within 72 hours by phone, and weekly contact with the BH-VPN until 45 days post ED discharge
 
• Confirm that a follow-up visit is scheduled and if the patient made it to the appointment.
 
• Placement into an appropriate case management program, if needed
 

Statistical Analysis
	
Analyses will include all patients identified as having completed telepsychiatric consult and meeting the additional inclusion and exclusion criteria. Comparisons of the intervention and usual care groups will be made using univariate analyses such as the t-test and chi-square test. The primary outcome, ED to inpatient conversion, will be compared between the two groups of patients using logistic regression. Results will be presented with odds ratios and 95% confidence intervals.

**LIST OF ABBREVIATIONS**

AMI	Any Mental Illness
BH-VPN	Behavioral Health Virtual Patient Navigation
CHS	Carolinas Healthcare System
CORE	Center for Outcomes Research and Evaluation
C-SSRS	Columbia – Suicide Severity Rating Scale
DHHS	Department of Health and Human Services
EHR	Electronic Health Record
ED	Emergency Department
EDW	Enterprise Data Warehouse
FY	Fiscal Year
HIIN	Hospital Improvement Innovation Network
NC	North Carolina
OCTR	Office of Clinical and Translational Research
PHI	Private Health Information
QCC	Quality, Comfort, and Care
SOP	Standard Operating Procedures

## **OBJECTIVES**

### **1.1. Hypothesis**

Patients who have had a telepsychiatric consultation in the ED and also receive behavioral health care navigation will have a lower ED to inpatient conversion than patients who receive usual care.

### **1.2. Primary Objective**

The primary objective is to evaluate the effectiveness of the use of a behavioral health – virtual patient navigation team compared to usual care, on the current ED encounter to inpatient conversion rate among patients with a completed telepsychiatric consult.

### **1.3. Secondary Objectives**

The secondary objectives are to examine the behavioral health – virtual patient navigation team’s effect on additional patient outcomes, such as the

- i. CHS Quality, Comfort, and Care 30-day readmission rate. This is a readmission rate among patients with an inpatient readmission to the same CHS facility as the index encounter. This measure applies to patients that have a hospital admission subsequent the ED encounter.
- ii. The patient-centric 30-day readmission rate. This is a readmission rate among patients with an inpatient or observation readmission to any CHS facility. This measure applies to patients that have a hospital admission subsequent the ED encounter.
- iii. 45-day post ED discharge utilization (ED, inpatient, observation encounters)
- iv. 90-day post ED discharge utilization (ED, inpatient, observation encounters)

## **2. BACKGROUND**

Hospital admissions are common amongst those with mental illness. Significant morbidity exists for patients who are being admitted to a psychiatric hospital from the Emergency Department (ED). Additionally, admission to a hospital setting may have adverse effects on patients psychologically, degrade relationships with therapists, and disrupt continuity of care. Based on verbal reports from psychiatrists providing virtual consults at Carolinas HealthCare System (CHS), providers often decide to admit to a psychiatric hospital because of limited availability of outpatient behavioral health resources.

The number of patients seeking psychiatric services continues to grow at the national, state, and system level. In 2015, there were an estimated 43.4 million adults aged 18 or older in the United States with AMI (Any Mental Illness) within the past year. This number represented 17.9% of all U.S. adults. In North Carolina, every 2.5 minutes a person in behavioral health crisis visits an ED. For Carolinas Healthcare System’s Metro EDs, Behavioral Health visits increased from 8,449 in 2011 to 14,293 in 2016 (internal report). In North Carolina’s FY12, 19,020 persons seeking help in an ED for a primary mental health, developmental disability, or suicide attempt issue accounted for 26,009 visits, a repeat visit rate of 27%. Thirteen percent of those re-admissions occurred within 30 days. (DHHS data analysis of NC Medicaid

Claims). Based on a Premier Quality Advisor Report that includes readmissions for 26 Carolinas Healthcare System hospitals, patients who have a primary behavioral health diagnosis demonstrated a 7% readmission rate in 2015.

As the number of behavioral health patients presenting to the acute care EDs for psychiatric care continues to increase, we find there is a significant need to find interventions that will avoid unnecessary admissions or readmissions of these patients. Through verbal reports, ED psychiatrists at CHS must make the decision to admit a patient because there is no one to facilitate an outpatient appointment, ensure medications are filled, or provide follow-up so the patient can be discharged. Hospital readmission within 30 days of discharge usually represents a negative clinical outcome for patients with mental disorders and may be due to factors such as poor access to adequate community-based aftercare and challenges in psychiatric medicine and self-care. Some of these challenges could be addressed by patient navigation, which has been shown to be effective. The largest suicide intervention trial in the U.S has shown a 30 percent reduction in suicide attempts over a 1 year follow-up as compared to standard care in the ED. This intervention utilized safety planning periodic check-ins via a phone call.

Carolinas Healthcare System's began utilizing telepsychiatry in 1997. The success of the virtual model led to the development of the robust program that exists today. The CHS virtual model currently offers 21 Metro EDs 24-7 access to licensed clinicians and psychiatrists who are able to provide psychiatric evaluations and dispositions. A 2007 study showed psychiatric consultation and short-term follow up provided by telepsychiatry can produce clinical outcomes that are equivalent to those achievable when patients are seen face to face.

The Hospital Improvement Innovation Network (HIIN) is a nationwide effort to reduce preventable hospital acquired conditions and hospital readmissions. Part of the HIIN effort surrounding behavioral health patients, includes identifying packages or key components most effective at preventing psychiatric admission and exploring ways to efficiently apply effective strategies. As a complement to the telepsychiatry program, a partnership has been formed with HIIN to develop a patient navigator program to provide short-term follow up to patients who are evaluated by telepsychiatry and potentially eligible for discharge home. The patient navigator will connect with the patient virtually prior to discharge from the ED and assist the patient in obtaining services and overcoming any barriers for 45 days post ED discharge.

By providing this wrap-around service to complement Carolinas HealthCare System's telepsychiatry program, we expect to decrease the number of patients admitted for inpatient psychiatric treatment and increase the number of discharges from the ED by providing another layer of service to our providers and patients. Additionally, we aim to decrease hospital inpatient admissions and increase after-care compliance with medications and appointments through short-term follow up. In one study regarding inpatient psychiatric care, it was found that patients who did not comply with at least one outpatient appointment after discharge were two times more likely to be readmitted than those who kept at least one appointment after discharge.

### **3. RATIONALE**

To enhance the care of patients with a telepsychiatric consult, Carolinas HealthCare System (CHS) has designed a Behavioral Health Virtual Patient Navigation pathway (BH-VPN). The BH-VPN will monitor patients and assist with navigation through a weekly phone call after their index ED encounter for up to 45 days post ED discharge. The BH-VPN aims to improve patient outcomes through standardized approaches that leverage analytics and technology, while bridging care coordination. When a patient presents to a participating CHS ED sites, those with a telepsychiatric consult completed on a randomized intervention day, during the hours of operation, are provided the option of participating in the BH-VPN. A patient can choose not to receive care by the navigator post discharge.

The BH-VPN pathway includes the following key components: introduction to the patient follow-up process prior to ED discharge, follow-up evaluation within 72 hours by phone and weekly contact, confirmation that a follow-up visit is scheduled, where applicable confirm in-network follow-up appointments are completed with a CHS provider, and placement into an appropriate case management program, if needed. There may be cases where patients are eligible to enroll in full case management programs based on their insurance and certain criteria. For example, if a patient has Medicaid through Cardinal Innovations, a managed care organization providing local behavioral health care, and meets certain criteria, and would no longer require navigation services. A patient's contact with the BH-VPN ends after 45 days following ED discharge, or if there is a failure to contact, becomes enrolled with a case-management program, declines services, or the patient dies. The navigator will ensure the patient is enrolled in a case management program through contact with staff before ending contact with the patient.

This research project is a pragmatic, randomized quality improvement evaluation which seeks to evaluate the effects of standardizing the use of a BH-VPN among patients with a telepsychiatric consult. The outcomes evaluation of this quality improvement intervention has been designed to integrate into the routine care and minimize frontline staff burden by deploying an evaluation in a real-world setting.

### **4. SUBJECT AND SITE SELECTION**

#### **4.1. Accrual**

As part of current care, patients are identified by an ED physician in the ED as needing psychiatric evaluation, and a referral is made to the telepsychiatric provider for a virtual consult. Patients are eligible to be included in analysis for the project if they meet the inclusion/exclusion criteria and the telepsychiatric consultation occurs during potential BH – VPN hours. We will accrue patient data for evaluation during a period starting in June 2017. Based on data from 2016, we estimate 500 patients will complete a telepsychiatric consult in a 6-month period during potential BH-VPN hours of operation. Patients will not be accrued on days where the navigators could not potentially be available, such as nights, weekends, and holidays.

Once a patient is in the intervention arm, the patient remains in the intervention arm until 45 days, or if there is a failure to contact (4 phone calls in 12 days), if the patient becomes enrolled with a case management program, declines services, or if the patient dies. After 45 days, a patient is eligible to be re-enrolled in either arm of the study.

A patient remains in the control arm for 45 days unless the patient returns to the ED on a day where patients are being randomized to the intervention arm.

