## **5.2. Randomization and Allocation**

Randomization for the purposes of this project, will be based on days the Navigators are available to treat patients who've completed their telepsychiatric consult per the BH-VPN or usual care. Patients may be in the ED for multiple days. Their enrollment status depends on the day and time of their initial telepsychiatric consultation. Navigation will only be available for those patients whose consult occurs during intervention day/times. As part of the research design and rollout of this project, randomization will occur at the day level with the days being identified as intervention or usual care days for the duration of the study. We expect an average of 3.7 patients seen daily for both hospitals combined. Patients will accrue in both arms of the study Monday through Friday during the hours of operation. Patients will not be accrued on days where the navigators are not available such as weekends, nights, and holidays.

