## 6.1. Sample size analysis and statistical analysis

We are conducting the study for about 6 months leading to approximately 6 months\*4 weeks\*5 days=120 days with 60 days allocated to intervention and 60 allocated to treatment as usual. This study is designed to detect a 15% absolute reduction in the inpatient admission within 5 days of index ED presentation with the usual care group assumed to have a 50% inpatient admission rate (internal report). We will have 85% power to detect this reduction with a total sample size of 414 ( $\alpha=0.05$ ) using a Chi-square test for independence. We will not need to adjust for attrition as the primary outcome of inpatient admission <5 days is obtainable from electronic health records for all individuals. To account for the possible correlation among patients seen in the ED on the same day, we have inflated the sample size by 10% assuming the average number of patients per ED per day is 2 and the intra-class correlation coefficient=0.1 (Design effect=1+(2-1)ICC). Therefore, our target sample size is N=456.

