## 6.2. Statistical analysis

All analyses will follow intention to treat such that patients will be analyzed based on the allocated intervention on the day of their ED visit (BH-VPN or treatment as usual). We will compare the two groups on age, sex, suicide ideation, and neurocognitive disorders to assess for balance, which is inferred with randomization.

The primary outcome, inpatient admission  $\leq 5$  days, will be compared between the two groups of patients using a chi-square test. We will explore differences by site by conducting stratified analysis by hospital. We will attempt to adjust for the correlation among patients seen on the same day using a generalized linear mixed model with a log link and random effect for day, nested within hospital. If convergence problems arise due to small sample sizes, we will collapse by week rather than day. We will also control for hospital as a fixed effect in the model. Results for group comparisons will be presented with odds ratios and 95% confidence intervals.

Secondary outcomes are 45-day post discharge utilization (yes/no), 90-day post discharge utilization (yes/no), QCC defined 30-day readmission (yes/no), and patient centric 30-day readmission (yes/no). Each of the secondary outcomes are dichotomous and will be compared using the same approach as the primary outcome. All tests will be two sided and the data will be analyzed using SAS Enterprise Guide version 6.1. For all outcomes, we assume if there are no visits in the CHS electronic medical record that the value for having a visit is null; therefore, there will be no missing data for the primary or secondary outcome measures.

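### Section 4.1 lets a return within 45 days move a patient from control to intervention but not the reverse, which conflicts with analysis by the day's allocation in 6.2

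*Combined protocol and SAP*

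**What the plan says.** Section 4.1 (Accrual) gives three rules for patients already in the study.

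- Intervention: "Once a patient is in the intervention arm, the patient remains in the intervention arm until 45 days". The listed earlier exits are failed contact, entry to case management, declining services and death. A return on a usual-care day is not among them.
- Control: "A patient remains in the control arm for 45 days unless the patient returns to the ED on a day where patients are being randomized"; the day meant is one allocated to intervention.
- Re-entry: "After 45 days, a patient is eligible to be re-enrolled in either arm of the study".

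Other sections classify patients differently. The Protocol Summary (Study Procedures) says that "on days the navigator is not available all patients will be considered exposed to Usual care", with no exception for patients already in the intervention arm. Section 6.2 applies intention to treat, so that "patients will be analyzed based on the allocated intervention on the day of their ED visit", but does not say which visit counts for someone who has several. Section 5.2 says "Their enrollment status depends on the day and time of their initial telepsychiatric consultation"; the context is an ED stay lasting several days, and later ED visits are not addressed. Section 5.5 lists how participation ends and does not include a control patient's return on an intervention day.

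Section 5.1.2 counts any inpatient, observation or ED encounter at a CHS facility as utilization, and section 6.2 analyses it as yes/no at 45 and 90 days. The mixed model in 6.2 has a random effect for day within hospital and a fixed effect for hospital. It has no term for patient.

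**The concern.** Randomising days makes the arms comparable if patients are classified by the same rule on both kinds of day. Under 4.1 they are not. Take two patients who each return on day 20. One was first seen on a usual-care day and returns on an intervention day: that patient leaves control. The other was first seen on an intervention day and returns on a usual-care day: that patient stays in intervention under 4.1, yet belongs to usual care under the Summary and, if the return is the visit that counts, under 6.2. Two analysts could build different analysis sets from the same extract.

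The event that triggers the change occurs after randomisation and is itself a study outcome, since a return to either participating ED is a utilization event. Two outcomes are possible, and the plan does not choose between them:

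- **Moved.** The first record leaves control. Control loses patients who have all had a utilization event, while intervention keeps its own returners.
- **Counted twice.** The same patient contributes to both arms, and the model treats the records as if they came from different people, apart from the shared-day effect. An admission after a return within 5 days could count for the control visit, the intervention visit, or both.

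**Working it through.** **The plan's own figure.** Section 6.1 assumes 50% against 35%, two-sided alpha 0.05 (two-sided from 6.2) and 85% power. The uncorrected two-proportion formula gives 194 per arm (388 in total). With the continuity correction it gives 207 per arm, or 414, as stated. The 10% clustering inflation gives 414 × 1.10 = 455.4, rounded up to 456, or 228 per arm. These figures are sound, and the point below does not change them.

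**Return rate.** No rate is given for these two EDs. Section 2 gives statewide figures: 26,009 visits by 19,020 persons, so (26,009 − 19,020)/26,009 = 26.9% of visits are repeats. Thirteen percent of those fell within 30 days (taking that sentence to refer to the repeat visits): 0.13 × 26.9% = 3.5% of visits. The window here is 45 days, but a return must also fall in navigator hours with a completed consult. I use an assumed share r of 3.5% to 20% with an eligible return.

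**Number crossing.** Section 6.1 has 120 days, "with 60 days allocated to intervention and 60 allocated to treatment as usual", so half of eligible returns fall on intervention days: x = 228 × r × 0.5. Under 4.1 the number crossing the other way is 0 at every r. Returners' share of intervention records is x/(228 + x).

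**Primary outcome with no true effect.** First visits convert at 50%.

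- Counted twice: shift = (114 + x·p)/(228 + x) − 0.50, with returners' conversion p assumed to be 60% to 70%.
- Moved: shift = (114 + x·p)/(228 + x) − (114 − x·q)/(228 − x), with p assumed to be 50% to 70% and the conversion q of the returners' first records 20% to 80%.

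**45-day utilization in control if patients are moved.** Assume 30% true utilization, so 68.4 events in 228. Every patient removed is an event: (68.4 − x)/(228 − x).

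| r | x | Share of intervention records | Primary, counted twice (points) | Primary, moved (points) | Control utilization, moved |
|---|---|---|---|---|---|
| 3.5% | 4.0 | 1.7% | +0.2 to +0.3 | −0.5 to +0.9 | 28.8% |
| 5% | 5.7 | 2.4% | +0.2 to +0.5 | −0.8 to +1.3 | 28.2% |
| 10% | 11.4 | 4.8% | +0.5 to +1.0 | −1.6 to +2.5 | 26.3% |
| 20% | 22.8 | 9.1% | +0.9 to +1.8 | −3.3 to +5.2 | 22.2% |

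Worked case at r = 10%: (68.4 − 11.4)/(228 − 11.4) = 57/216.6 = 26.3%, a fall of 3.7 points from 30% with no treatment effect. If none of the 11.4 moved patients had a further event, intervention would read 68.4/239.4 = 28.6%, still above control.

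**Check by simulation.** I simulated 120 weekdays split 60/60 with 456 first visits. Here r is the share returning on any day within 45 days, and returns at weekends or after accrual ends are lost. Crossings to intervention were 3.5, 7.1 and 14.1 at r = 5%, 10% and 20%, with none to usual care. When each return was classified by its own day, returns balanced: 14.1 against 14.1 at 10%, and 28.0 against 28.1 at 20%.

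**The case against.** The strongest reply is that 4.1 describes who is receiving navigation, not who is analysed in which arm. Its intervention exits are nearly the same events that end navigator contact in section 3 and participation in 5.5. If they set analysis membership, a patient who declined would leave the intervention arm, contrary to the intention-to-treat statements in 4.4 and 6.2. On that reading the asymmetry is natural, and 6.2 could be taken to classify every visit by its own day, which is symmetric.

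This is plausible but not decisive. The rules sit under Accrual and are worded in terms of arms and re-enrolment. No section says that 6.2 overrides them or which visit counts for a returner.

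Other parts of the reply stand. A reader might infer that the rule biases the primary result against navigation. The documents do not support a direction: if patients are moved and their first records were mostly non-conversions, their removal raises the control rate and favours navigation. A reader might also take the 27% repeat rate as the relevant return rate. It is statewide and not limited to 45 days, and the next sentence in section 2 points to the low end of the range. Finally, re-enrolment after 45 days might look like part of the same fault. It is open to either arm according to the day, so it does not load one arm, although it does produce repeat records for the same patient.

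**Conclusion.** The point holds as a conflict in the plan that leaves arm membership undefined for returning patients and, if 4.1 is followed in the analysis, makes it depend on a post-randomisation event in one direction only. About 4 to 23 of 228 control patients would cross at assumed eligible return rates of 3.5% to 20%, and none the other way.

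For the primary outcome the likely distortion is small beside the 15-point design effect. At 10% returning it is +0.5 to +1.0 points if records are added and −1.6 to +2.5 if patients are moved, with no established direction. The 45- and 90-day utilization outcomes are the firmer concern, because moving patients strips certain events from control. The size of that loss rests on the assumed return rate and the assumed 30% utilization.

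The documents do not show that a biased analysis will be run, or that the primary conclusion would be overturned. The change should be made because it is cheap and settles who is in each arm; it is not a fatal flaw.

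**What to change.** In 4.1, 4.4 and 6.2, state that the control exit and the 45-day retention rule do not determine analysis membership. Define one analysis unit for both arms: the first eligible telepsychiatric consult per patient, kept in that day's randomised arm for the 5-day, 30-day, 45-day and 90-day outcomes. Later visits count only as outcomes of that consult. Reconcile the Protocol Summary and 5.2 with this wording.

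As a sensitivity analysis, classify every eligible consult by its own day's allocation in both arms, and account for repeated consults by the same patient.

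Whether a returning patient is offered navigation is left to the site. A control patient navigated after a return stays in control for analysis. The yes/no utilization outcomes are unaffected by this, because the return has already made them positive, but the number of such patients should be reported.

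The cost is wording in these sections and a de-duplication step in the extract. The targets of 414 and 456 do not change. Repeat consults no longer add to the analysed number, so the 500 expected in 4.1 should be confirmed as unique patients.
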